##### ***8.4.2 ClinicalTrials.gov Requirements***

The project is registered on ClinicalTrials.gov (NCT # NCT05007014)

#### ***8.5 Human Subjects***

In obtaining and documenting informed consent, the Investigator and study team will comply with the applicable regulatory requirements, Good Clinical Practices, and ethical principles. The written informed consent form must be signed and dated by the study participant prior to initiation of any study activities.

### **8.5.1 Vulnerable Subjects Research**

This study proposes to include subjects with mild cognitive impairment. All potential subjects will undergo cognitive assessment to ensure they are capable of providing consent. Mild cognitive impairment is a common age-related condition that is defined by the presence of short-term memory impairment that does not interfere the individual's ability to perform activities of daily living or affect other areas of cognition, including judgment and independent decision-making. Therefore, persons with mild cognitive impairment have the capacity to make decisions about their health care choices, including influenza vaccination, and participation in research studies. Influenza vaccination is recommended for these individuals. The benefits and burdens of the proposed study apply equally to these individuals as to persons without mild cognitive impairment.

Potential participants may have low scores on the cognitive screening tests and be ineligible for the study. In this case, the study doctor or designee will review the results with the individual and recommend follow-up with the individual's health care provider.

## Appendix

1 INTRODUCTION

This document describes the statistical procedures that will be utilized for the CISA protocol Safety of Simultaneous Vaccination with Zoster Vaccine Recombinant (RZV) and Quadrivalent Adjuvanted Inactivated Influenza Vaccine (allIV4) that was approved on September 7, 2022. This statistical analysis plan (SAP) describes the methods of statistical analysis. The initial draft SAP (Version 0.1) was developed prior to any data being analyzed in order to avoid bias. Any subsequent changes that occur to the study protocol warranting changes to the analysis procedures will be documented in the SAP (both draft versions (0.X) and the final version (X.0). Table 1 below will be used for tracking of changes to the SAP. In this study of 400 adults age ≥ 65 years, participants aged 65 to 69 years will be randomized (1:1) to receive either simultaneous RZV and allIV4 or RZV and HD-IIV4 using a permuted block randomization scheme stratified by Lead and Contributing Site. A separate permuted block, stratified by site will be allocated for subjects who are age 70 years and older.

Table 1. Statistical Analysis Plan Versions

Version	Date of Approval	Major Changes from Prior Version
0.1	TBD	NA
0.2	TBD	Section 3.3 – Exploratory objective # 7: Specified sample collection dates Section 8.1. – Primary Objective: Corrected age range
0.3	TBD	Added Under Study Objective Outcomes (SO1, SO2, EO1, EO2, EO3, EO5, and EO6): This information will also be presented by age-group for the subset of subjects aged 65-69 versus those subjects aged 70 years or older. No formal statistical hypothesis testing (i.e., no p-values) will be performed, only the confidence boundary of the difference will be presented. Added minor edits Added EQ-5D & EQ VAS Post-vaccination score description
1.0	11/27/2022	Minor edits provided by the CDC
2.0	5/7/2024	Corrected minor typo in description of EO4 in Section 8.3 Corrected minor typo in description of SO1 in Section 3.2

2 PROTOCOL OBJECTIVES

2.1 Primary

1. To compare the proportion of participants with at least one severe (Grade 3) solicited local or systemic reactogenicity event after RZV dose 1 in the RZV and allV4 group vs. RZV and HD-IIV4 group.
 - Hypothesis: The proportion of participants with at least one severe (Grade 3) solicited reactogenicity event after RZV dose 1 will be noninferior (not higher) in the RZV and allV4 group compared with the RZV and HD-IIV4 group.

2.2 Secondary

1. To compare the proportion of participants with at least one severe (Grade 3) solicited local reactogenicity event after RZV dose 1 in the RZV and allV4 group vs. RZV and HD-IIV4 group.
2. To compare the proportion of participants with at least one severe (Grade 3) solicited systemic reactogenicity event after RZV dose 1 in the RZV and allV4 group vs. RZV and HD-IIV4 group.
3. To compare the proportion of participants with at least one serious adverse event or adverse event of clinical interest after RZV dose 1 in the RZV and allV4 group vs. RZV and HD-IIV4 group through Day 43 and describe these events.

2.3 Exploratory

1. To compare the proportion of participants with at least one severe (Grade 3) solicited local or systemic reactogenicity event after RZV dose 2 in the RZV and allV4 group vs. RZV and HD-IIV4 group.
2. To compare the proportion of participants with at least one severe (Grade 3) solicited local reactogenicity event after RZV dose 2 in the RZV and allV4 group vs. RZV and HD-IIV4 group.
3. To compare the proportion of participants with at least one severe (Grade 3) solicited systemic reactogenicity event after RZV dose 2 in the RZV and allV4 group vs. RZV and HD-IIV4 group.
4. To compare the proportion of participants with at least one serious adverse event or adverse event of clinical interest after RZV dose 2 in the RZV and allV4 group vs. RZV and HD-IIV4 group and describe these events through the entire study period.
5. To compare the proportion of participants with moderate-to-severe (Grade 2-3) solicited local or systemic reactogenicity event after RZV dose 1 in the RZV and allV4 group vs. RZV dose 1 and HD-IIV4 group.
6. To compare the proportion of participants with moderate-to-severe (Grade 2-3) solicited local or systemic reactogenicity event after RZV dose 2 in the RZV and allV4 group vs. RZV and HD-IIV4 group.
7. To compare serum hemagglutination inhibition (HAI) antibody titers after RZV dose 1 and HD-IIV4 with RZV dose 1 and allV4 for each of the four influenza vaccine strains contained in the respective vaccine for that season in the full study population and by age.
8. To describe and compare changes in health-related quality of life after RZV dose 1 and allV4 with RZV dose 1 and HD-IIV4 in the full study population and by age group.

3 STUDY ENDPOINTS/OUTCOME MEASURES

3.1 Primary

1. Proportion of subjects reporting at least one severe (grade 3) solicited local or systemic reactogenicity event on days 1-8 after RZV dose 1 in each study group.

3.2 Secondary

1. Proportion of participants with at least one severe (grade 3) solicited local reactogenicity event on days 1-8 after RZV dose 1 in each study group.
2. Proportion of participants with at least one severe (grade 3) solicited systemic reactogenicity event on days 1-8 after RZV dose 1 in each study group.
3. Proportion of participants with at least one serious adverse event or adverse event of clinical interest after RZV dose 1 and clinical description of these events in each study group through Day 43.

3.3 Exploratory

1. Proportion of participants with at least one severe (grade 3) solicited local or systemic reactogenicity event on days 1-8 after RZV dose 2 in each study group.
2. Proportion of participants with at least one severe (grade 3) solicited local reactogenicity event on days 1-8 after RZV dose 2 in each study group.
3. Proportion of participants with at least one severe (grade 3) solicited systemic reactogenicity event on days 1-8 after RZV dose 2 in each study group.
4. Proportion of participants with serious adverse events and adverse events of clinical interest after RZV dose 2 and clinical description of these events in each study group through the entire study period.
5. Proportion of participants with at least one moderate-to-severe (Grade 2-3) solicited local or systemic reactogenicity event on days 1-8 after RZV dose 1 in each study group.
6. Proportion of participants with at least one moderate-to-severe (Grade 2-3) solicited local or systemic reactogenicity event on days 1-8 after RZV dose 2 in each study group.
7. HAI titers by vaccination group and age group:
 - a. The proportion of subjects achieving seroconversion at day 29 (an HAI titer \geq 1:40 at day 29 if the baseline titer is $< 1:10$ or a minimum four-fold rise in HAI titer if the baseline titer is $\geq 1:10$) for each influenza strain in the respective season's vaccine.
 - b. Proportion of subjects with a seroprotective HAI titer ($\geq 1:40$) pre- and post-immunization at day 29 for each IIV antigen in the respective season's vaccine.
 - c. The geometric mean HAI titer (GMT) at baseline (Day 1) and Day 29 for each IIV antigen in the respective season's vaccine.
 - d. The geometric mean fold rise (GMFR) in HAI titer at Day 29 for each IIV antigen in the respective season's vaccine.
8. Change in scores on the EuroQOL 5 dimensions-5 level (EQ-5D-5L) and EuroQOL visual analogue scale (EQ VAS) pre-vaccination and post-vaccination will be compared between the vaccination groups and age groups.

4 STUDY DESIGN

4.1 Main Study Description

This study is a prospective, randomized, blinded clinical trial to assess the safety of simultaneous RZV and allIV4 versus simultaneous RZV and HD-IIV4 in 400 adults age ≥ 65 years. Older adults who have not received RZV (Shingrix vaccine) or IIV during the 2021-2022 and 2022-2023 influenza seasons will be enrolled; participants enrolling in the 2022-2023 influenza season may have received influenza vaccine in the prior season. Detailed health and demographic data will be collected from study participants at baseline prior to influenza vaccine receipt. With Day 1 serving as the day of vaccination, participants will be followed through Day 8 (total 8 days) for symptoms of reactogenicity. Vaccinations will be performed by unblinded study staff with all follow-up assessments being conducted by blinded staff. Study subjects will be blinded throughout the study. Participants will be followed through Day 43 after each dose of RZV for adverse events and adverse events of clinical interest, including

health care utilization, and through the entire period of enrollment for serious adverse events and immune-mediated conditions (see Appendix A).

4.2 Laboratory

4.2.1 Influenza Hemagglutination Inhibition Assay

Participants will have blood draws on Day 1 (before vaccination) and Day 29 to be stored for serum hemagglutination inhibition (HAI) antibody titers. HAI antibody titers will be compared between groups receiving allV4 or IIV4-HD for each of the four influenza vaccine strains contained in the respective vaccines for that season.

4.3 Sample Size and Power

Safety: Based on information from the pre-licensure trials for RZV, we assume that 14% of adults ≥ 65 years will have at least one severe solicited local or systemic reactogenicity event after RZV dose 1. We have selected a clinically meaningful noninferiority margin of 10%. Statistical calculations, without consideration for study drop-out, show that with a one-side alpha level of 0.025, we would need 380 total subjects (190 subjects in each group across all study sites) to have at least 80% power to be able to demonstrate that the proportion of adults ≥ 65 years with at least one severe solicited local or systemic reactogenicity event after RZV dose 1 is noninferior after RZV and allV4 versus RZV and HD-IIV4. Assuming a 5% drop out rate, we plan to recruit and randomize 400 total subjects.

4.4 Randomization

Participants aged 65 to 69 years will be randomized (1:1) to receive either simultaneous RZV and allV4 or RZV and HD-IIV4 using a permuted block randomization scheme stratified by Lead (Duke University) and Contributing Site (Johns Hopkins University). A separate permuted block will be allocated for subjects who are age 70 years and older. The project statistician will generate permuted block randomization schemes, which will be uploaded to REDCap (see below). The randomization schedule will not be available to the study staff, so the next randomization allocation will not be known before randomization occurs. Following confirmation of study eligibility criteria during Visit 1, participant randomization will be through REDCap with treatment allocation recorded on the case report form (CRF).

In the event that REDCap is unavailable, manual randomization will occur through the use of envelopes. The project statistician will prepare 20 envelopes per participant age group per site (total of 40 per site) that will use the same randomization strategy as the primary scheme embedded in REDCap. When an unblinded team member is informed of the participant's age group, he/she will pull the next envelope in order. In order to capture the allocation per subject, a separate form in REDCap will be used by the unblinded personnel to add the assignment. A log will need to be kept at the site capturing these instances.

5 PARAMETERS OF ANALYSIS

5.1 Data Collection and Storage

The novel Vanderbilt-designed resource developed specifically for online collection of research information, the Research Electronic Data Capture (REDCap) platform (<https://projectredcap.org/>), will be used to design study forms, including the case report forms, adverse event forms, and short customized questionnaires to collect information from study subjects. REDCap provides: 1) a streamlined process for rapidly building a database; 2) an intuitive interface for collecting data, with data validation and audit trail; 3) automated export procedures for seamless data downloads to common statistical packages; 4) branching logic, file uploading, and calculated fields; and 5) a quick and easy protocol set-

up. This system will be used by Duke for data management. All electronic linkages will fulfill regulations for protection of human subjects and requirements to minimize the risk of breach of confidentiality.

All study-related documents containing protected health information, e.g., enrollment logs, case report forms, diaries completed by study participants, will be maintained in secure research offices at Duke and Johns Hopkins University, which are accessible to research staff only.

The study team will utilize a secure, encrypted, file transfer method for sharing study documents and data with the CDC. No personal identifiers will be included in any shared documents or datasets.

5.2 Analytic Issues

There are two sites participating in the study and analysis of the primary objective will be stratified by site (Duke University and Johns Hopkins University) to account for this unit of randomization. All objectives will be stratified by site when applicable. The alpha will be set at a one-sided 0.025 level for noninferiority testing and at the alpha 0.05 level otherwise. There will be no adjustments to the alpha level for multiple comparisons. Should an interim safety analysis be required, the alpha level will be adjusted to assure the overall type I error is maintained at the one-sided alpha 0.025 level for the primary outcome of non-inferiority.

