**5.2.1 Randomization**

Participants aged 65 to 69 will be randomized (1:1) to receive either simultaneous RZV / allV4 or RZV / HD-IIV4 using a permuted block randomization scheme stratified by Lead and Contributing Site. A separate permuted block will be allocated for subjects who are age 70 or older. The project statistician will generate permuted block randomization schemes, which will be uploaded to REDCap. The randomization schedule will not be available to the study staff, so the next randomization allocation will not be known before randomization occurs. Following confirmation

of study eligibility criteria during Visit 1, participant randomization will be through REDCap with treatment allocation recorded on the CRF.

In the event that REDCap is unavailable, manual randomization will occur through the use of envelopes. The project statistician will prepare 20 envelopes per participant age group per site (total of 40 per site) that will use the same randomization strategy as the primary scheme embedded in REDCap. When an unblinded team member is informed of the participant's age group, he/she will pull the next envelope in order. In order to capture the allocation per subject, a separate form in REDCap will be used by the unblinded personnel to add the assignment. A log will need to be kept at the site capturing these instances.

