#### Immunogenicity Population:

For Exploratory Objectives 7 and 8 (immunogenicity analyses) the primary analysis population will be the Immunogenicity Population 2; defined as subjects who received vaccine, provide baseline and Visit 4 blood draws of acceptable volume and quality within the protocol-defined time frame with no protocol violations affecting immunogenicity. Protocol violations affecting the immunogenicity analyses will be defined in the Statistical Analysis Plan (SAP).

### 7.1.3 Primary Objective 1

- To compare the proportion of older adults with at least one severe (Grade 3) solicited local or systemic reactogenicity event after RZV dose 1 in the RZV and allV4 group vs. RZV and HD-IIV4 group.
  - Hypothesis: The proportion of participants with at least one severe (Grade 3) solicited reactogenicity event after RZV dose 1 will be noninferior (not higher) in the RZV and allV4 group compared with the RZV and HD-IIV4 group

This objective will be assessed using a one-sided noninferiority test with the alpha level set at 0.025 and noninferiority margin of 10%. The null hypothesis is RZV and allV4 is inferior (i.e., RZV and allV4 will have a higher proportion) to RZV and HD-IIV4 in regards to the proportion of adults with at least one severe (Grade 3) solicited local or systemic reactogenicity event after RZV dose 1.

$$H_0: RZV \text{ and allV4} - RZV \text{ and HD-IIV4} \geq 0.10 \text{ (10\%)}$$

The alternative hypothesis is RZV and allV4 is noninferior to RZV and HD-IIV4 in regards to the proportion of adults with at least one severe (Grade 3) solicited local or systemic reactogenicity event after RZV dose 1.

$$H_a: RZV \text{ and allV4} - RZV \text{ and HD-IIV4} < 0.10 \text{ (10\%)}$$

The upper bound of a site-stratified Newcombe binomial confidence interval with Cochran-Mantel-Haenszel (CMH) weighting of the difference will be used to make this assessment (29).

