8 ANALYSIS OF STUDY OBJECTIVES

8.1 Primary Objective

1. To compare the proportion of older adults with at least one severe (Grade 3) solicited local or systemic reactogenicity event after RZV dose 1 in the RZV and allV4 group vs. RZV and HD-IIV4 group

- Hypothesis: The proportion of participants with at least one severe (Grade 3) solicited reactogenicity event after RZV dose 1 will be noninferior (not higher) in the RZV and allV4 group compared with the RZV and HD-IIV4 group

This objective will be assessed in the mITT Population using a one-sided site-stratified noninferiority test with the alpha level set at 0.025 and noninferiority margin of 10%. The null hypothesis is simultaneous vaccination with RZV and allV4 is inferior (i.e., RZV and allV4 will have a higher proportion) to RZV and HD-IIV4 with regard to the proportion of adults with at least one severe (Grade 3) solicited local or systemic reactogenicity event on days 1-8 after RZV dose 1.

$$H_0: RZV \text{ and allV4} - RZV \text{ and HD-IIV4} \geq 0.10 \text{ (10\%)}$$

The alternative hypothesis is RZV and allV4 is noninferior to RZV and HD-IIV4 with regard to the proportion of adults with at least one severe (Grade 3) solicited local or systemic reactogenicity event after RZV dose 1.

$$H_a: RZV \text{ and allV4} - RZV \text{ and HD-IIV4} < 0.10 \text{ (10\%)}$$

The upper bound of a site-stratified Newcombe binomial confidence interval with Cochran-Mantel-Haenszel (CMH) weighting of the difference will be used to make this assessment.

This information is captured on the symptom diary CRF in the REDCap database. The grading criteria for injection site pain is provided in Tables 1 and 2.

Table 1. Injection-site Reactogenicity

Symptom	Mild (Grade 1)	Moderate (Grade 2)	Severe (Grade 3)
Pain	Any pain neither interfering with nor preventing normal every day activities.	Painful when limb is moved and interferes with every day activities.	Significant pain at rest. Prevents normal every day activities.
Induration/ Swelling	$\geq 20 \text{ mm to } \leq 50 \text{ mm diameter}$	$> 50 \text{ mm to } \leq 100 \text{ mm diameter}$	$> 100 \text{ mm diameter}$
Erythema (Redness)	$\geq 20 \text{ mm to } \leq 50 \text{ mm diameter}$	$> 50 \text{ mm to } \leq 100 \text{ mm diameter}$	$> 100 \text{ mm diameter}$

Table 2. Systemic Reactogenicity

Systemic	Mild (Grade 1)	Moderate (Grade 2)	Severe (Grade 3)

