8.2 Secondary Objectives

1. To compare the proportion of participants with at least one severe (Grade 3) solicited local reactogenicity event on days 1-8 after RZV dose 1 in the RZV and allIV4 group vs. RZV dose 1 and HD-IIV4 group.

The proportions of participants with at least one severe (Grade 3) solicited local reactogenicity event on days 1-8 after RZV dose 1 in the mITT Population will be compared between vaccine groups using the same statistical methodology as for Primary Objective 1. A one-sided site-stratified noninferiority test to determine if RZV dose 1 and allIV4 is noninferior to RZV dose 1 and HD-IIV4 with the alpha level set at 0.025 and a 10% noninferiority margin.

This information will also be presented by age-group for the subset of subjects aged 65-69 versus those subjects aged 70 years or older. No formal statistical hypothesis testing (i.e., no p-values) will be performed, only the confidence boundary of the difference will be presented.

2. To compare the proportion of participants with at least one severe (Grade 3) solicited systemic reactogenicity event on days 1-8 after RZV dose 1 in the RZV and allIV4 group vs. RZV dose 1 and HD-IIV4 group.

The proportions of participants with at least one severe (Grade 3) solicited systemic reactogenicity event on days 1-8 after RZV dose 1 in the mITT Population will be compared between vaccine groups using the same statistical methodology as for Primary Objective 1. A one-sided site-stratified noninferiority test to determine if RZV dose 1 and

allV4 is noninferior to RZV dose 1 and HD-IIV4 with the alpha level set at 0.025 and a 10% noninferiority margin.

This information will also be presented by age-group for the subset of subjects aged 65-69 versus those subjects aged 70 years or older. No formal statistical hypothesis testing (i.e., no p-values) will be performed, only the confidence boundary of the difference will be presented.

3. To compare the proportion of participants with at least one serious adverse event or adverse event of clinical interest after RZV dose 1 in the RZV and allV4 group vs. RZV dose 1 and HD-IIV4 group through Day 43 and describe these events.

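### The primary noninferiority bound is stratified by site only, although randomization is stratified by site and age group; the effect is small

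*SAP*

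**What the plan says.** **Randomization.** SAP 4.4 and Protocol 5.2.1 randomize 65-69-year-olds 1:1 in permuted blocks within each site. For the older group, SAP 1 says: "A separate permuted block, stratified by site will be allocated for subjects who are age 70 years and older". SAP 4.4 repeats this without mentioning site: "A separate permuted block will be allocated for subjects who are age 70 years and older". The backup envelopes in Protocol 5.2.1 settle the point, since there are "20 envelopes per participant age group per site (total of 40 per site". The scheme has four strata.

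**Analysis.** SAP 5.2 gives the reason for stratifying by site: "analysis of the primary objective will be stratified by site (Duke University and Johns Hopkins University) to account for this unit of randomization". It adds: "All objectives will be stratified by site when applicable". For the primary test, SAP 8.1 says: "This objective will be assessed in the mITT Population using a one-sided site-stratified noninferiority test with the alpha level set at 0.025". Protocol 7.1.3 specifies: "The upper bound of a site-stratified Newcombe binomial confidence interval with Cochran-Mantel-Haenszel (CMH) weighting of the difference will be used". Secondary objectives 1 and 2 and exploratory objectives 1, 2, 3, 5 and 6 reuse the method; the groups "will be compared between vaccine groups using the same statistical methodology as for Primary Objective 1" (SAP 8.2, and likewise 8.3).

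Two other places are also site-only: the between-group tests for exploratory objective 7 in Protocol 7.1.4, and the categorical VAS comparison for exploratory objective 8 in SAP 8.3.

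**Age.** SAP 8.1 to 8.3 present the reactogenicity results separately for 65-69 and 70 or older, with confidence bounds and no tests. Exploratory objectives 7 and 8 are also shown by age.

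**The concern.** The reason SAP 5.2 gives for using site, that it was part of the randomization, applies equally to age group by inference. Neither document explains the omission. The protocol also treats age as prognostic: Protocol 1.1 says grade 3 reactions became less frequent with age, citing any grade 3 event in 17% of recipients aged 50 or older and 12% of those aged 70 or older.

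The by-age displays do not fill the gap, because none of them adjusts the overall bound that decides noninferiority. Permuted blocks balance age when subjects are randomized. The primary population is mITT, though, and it drops randomized subjects who do not supply one complete diary day (SAP 6.2). Age balance in the analysed set is therefore likely but not assured. If the aIIV4 arm lost more of its younger, more reactogenic subjects, a site-only bound would make noninferiority slightly easier to declare in a safety trial.

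**Working it through.** **1. The plan's sample size (SAP 4.3).** Inputs: 14% in both arms, margin 0.10, one-sided alpha 0.025, power 80%.

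n per arm = (z₀.₉₇₅ + z₀.₈₀)² × 2 × 0.14 × 0.86 / 0.10² = (1.95996 + 0.84162)² × 0.2408 / 0.01 = 189.001, rounded up to 190.

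Power at 190 per arm is 80.2%, and 380 / 0.95 = 400. The stated figures reproduce.

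**2. Assumptions the documents do not supply.** They give no rate for ages 65-69 and no age mix. The ranges used were:
- 65-69 share s of 30, 50 or 70%;
- age contrast c of 0, 5 or 10 points;
- overall rate held at 14%, so the 65-69 rate is 0.14 + (1 − s)c and the 70-or-older rate is 0.14 − sc. With s = 50% and c = 5 points these are 16.5% and 11.5%.

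**3. The interval.** CMH weights are w ∝ n₁n₀/(n₁ + n₀), with stratified Wilson limits U₁ (aIIV4, upper) and L₀ (HD-IIV4, lower). The plan does not write out how the limits are combined, so two forms were run. With d the weighted difference:
- A: d + z√[λ₁U₁(1 − U₁) + λ₀L₀(1 − L₀)], where λ = Σw²/n;
- B: d + √[(U₁ − p₁)² + (p₀ − L₀)²].

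Two strata (site) and four strata (site by age group) were applied to the same simulated trials. Power was taken at zero difference and type I error at +10 points in every stratum.

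**4. Arms balanced on age.** 105 Duke and 85 Johns Hopkins per arm (the 220:180 split in Protocol 4.3), 200,000 trials per scenario. Monte Carlo error is 0.09 points for power and 0.035 for type I error.
- Site-only power: 79.5-79.9%.
- Change with four strata, form A: 0.0 to −0.2 points.
- Change with four strata, form B: +0.6, +0.4 and −0.2 points at c = 5 (s = 30, 50, 70%); at most +1.1 or −0.9 points at c = 10.
- Type I error: 2.5-2.7% site-only, 2.5-2.8% with four strata.

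A separate run of form A used 17% for ages 65-69, 12% for 70 or older and a 50:50 mix. (The documents give the 17% for ages 50 or older, so its use here is an assumption.) Power was 78.7% under both stratifications, and about 0.003% of trials changed conclusion.

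**5. Worst case with equal mITT losses.** 110 and 90 randomized per arm by site. The plan's 5% loss is taken as 10 exclusions per arm (6 Duke, 4 Johns Hopkins), all aged 65-69 in one arm and all 70 or older in the other. The 65-69 share then differs by 10/190 = 5.3 points. The site-only difference shifts by (10/190) × 0.05 = 0.26 points, or (10/190) × 0.10 = 0.53 points. The four-stratum difference does not shift. With 300,000 trials per scenario (Monte Carlo error 0.07 and 0.03 points):

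| Contrast | Quantity | Site-only, aIIV4 loses 70+ | Site-only, aIIV4 loses 65-69 | Four strata |
|---|---|---|---|---|
| 5 points | Power | 77.4-77.7% | 81.7-82.0% | 79.1-80.4% |
| 5 points | Type I error | 2.2% | 3.0-3.1% | 2.5-2.7% |
| 10 points | Power | 75.3-75.9% | 83.6-84.0% | 78.3-81.3% |
| 10 points | Type I error | 1.8-1.9% | 3.4% | 2.4-2.7% |

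Exclusions unrelated to age and arm bring the results back close to step 4.

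**The case against.** The strongest case on the other side concerns weight. The planned inference is valid. SAP 5.2 explains why site is used without claiming to cover every randomization factor, and age is examined in separate displays. With balanced arms almost nothing changes, and four strata can cost a little power.

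The visible effects come from an extreme construction. If exclusions were independent of age and arm at a 50:50 mix, the chance of it is about 2 × 0.5²⁰, or 2 in a million. The between-arm difference in 65-69 share would then have a standard deviation of about 1.2 points, which shifts the estimate by about 0.06 points at a 5-point contrast. The documents do not equate drop-out with mITT exclusion, subjects are blinded, and a reminder and a diary-review call support diary completion.

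A 10-point contrast also looks high. Taking the 12% at 70 or older as a rough guide and 14% overall gives (14 − 12)/s = 6.7, 4.0 or 2.9 points for s = 30, 50 or 70%.

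All of this stands, and it is why the point is minor and step 5 is only a bound. It does not supply the missing reason for leaving age group out, and the by-age displays still do not adjust the deciding bound. It is also fair that the objective 7 tests appear only in Protocol 7.1.4. SAP 8.3 gives differences and intervals for that objective without naming those tests, and the protocol makes the assays depend on funding.

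**Conclusion.** The point holds and is minor. Four strata were used to randomize, two are used to analyse, and the documents give no reason for the difference. The sample size is unaffected and the site-only analysis remains valid. With age-balanced arms the choice moves power by about one point at most, in either direction, and leaves type I error essentially unchanged. Only strongly age- and arm-dependent mITT losses would matter, and then by an excess of about 0.5 to 0.9 points over the nominal 2.5% one-sided error. These sizes rest on the assumed age mix, age contrast and interval form, and on counting all of the planned 5% loss as mITT exclusion. The gain from four strata is agreement with the randomization and protection of the bound if the analysed arms differ in age.

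**What to change.** **If treatment codes are still closed.** In SAP 5.2, 8.1, 8.2 and 8.3 and Protocol 7.1.3, stratify the between-group noninferiority interval by site and age group (65-69, 70 or older). Keep the site-only interval as a sensitivity analysis. Make the same change to the exploratory objective 7 Mantel-Haenszel comparisons and regression in Protocol 7.1.4, and to the categorical VAS comparison in SAP 8.3. Leave the by-age displays stratified by site alone. Enter the change and its date in the SAP version table.

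**If codes are already open.** Keep the site-only analysis as primary, report the four-stratum interval as a sensitivity analysis, and state in SAP 5.2 why age group is left out. SAP version 2.0 is dated 5/7/2024, after both planned influenza seasons, so the timing of any change must be documented.

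**Cost.** Wording changes and one variable already recorded. With a 70:30 age mix the smaller strata hold about 26 to 32 subjects per arm (0.3 × 85 and 0.3 × 105), and the four-stratum interval lost up to 0.9 points of power in the simulations.
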